6.2	Eligibility Criteria	11
6.2.1	Inclusion Criteria	11
6.2.2	Exclusion Criteria	11
6.3	Informed Consent Process	12
6.4	Enrolment and Randomisation Procedures	12
6.5	Blinding Arrangements	12
6.6	Breaking of the Study Blind	13
6.6.1	On Study	13

6.7.2	Replacements	13
7	STUDY VISITS AND PROCEDURES SCHEDULE	14
8	CLINICAL AND LABORATORY ASSESSMENTS	14
9	ADVERSE EVENT REPORTING	15
9.1	Definitions	15
9.1.1	Adverse Event (AE)	15
9.1.2	Adverse Reaction (AR)	15
9.1.3	Adverse Device Effect (ADE)	15
9.1.4	Device Adverse Event (DAE)	15
9.1.5	Expected Occurrence (EO)	15
9.2	Assessment and Documentation of Adverse Events	15
10	Serious Adverse Event Reporting	16
10.1	Definitions	16
10.1.1	Serious Adverse Event (SAE) / Serious Adverse Reaction (SAR)	16
10.1.2	Suspected Unexpected Serious Adverse Reaction (SUSAR)	16
10.1.3	Serious Adverse Device Effect (SADE)	16
10.1.4	Unanticipated Serious Adverse Device Effect (USADE)	16
10.1.5	Anticipated Serious Adverse Device Effect (ASADE)	16
10.1.6	Significant Safety Issue (SSI)	17
10.2	Eliciting Serious Adverse Event Information	17
11	STATISTICAL METHODS	17
11.1	Sample Size Estimation	17
11.2	Population to be analysed	17
11.3	Statistical Analysis Plan	17
11.4	Interim Analyses	17
12	DATA MANAGEMENT	18
12.1	Data Collection	18
13	ADMINISTRATIVE ASPECTS	19
14	USE OF DATA AND PUBLICATIONS POLICY	19
15	REFERENCES	21

PROTOCOL SYNOPSIS

Title	The TAI Study
Objectives	
Primary: To determine the effect of transanal irrigation (versus standard bowel care) on time to complete toileting.
 
Secondary: To determine the effect of transanal irrigation (versus standard bowel care) on the incidence of faecal incontinence, constipation and quality of life.

Study Design	Pragmatic, single blinded, randomised controlled trial
Planned Sample Size	24 (12 in each group)
Selection Criteria	
People will be eligible for inclusion if they:
 
 • have sustained a spinal cord injury more than 6 months prior or have Spina Bifida • have a Neurogenic Bowel Dysfunction Score (3) ≥ 3 • are aged 18 years or over at the time of consent • are willing to participate in the trial • have been recommended to trial transanal irrigation by a clinician because they spend more than 30 minutes on toileting AND ANY ONE OF THE FOLLOWING: 
 ○ had more than 1 episode of faecal incontinence per month ○ had a Bristol stool chart result of <3 or >6 for more than 3 cycles of bowel care ○ experienced abdominal symptoms such as bloating/cramping ○ experienced inconsistency with defaecation ○ experienced rectal symptoms (bleeding haemorrhoids, rectal prolapse, fissures etc) ○ experienced autonomic dysreflexia in response to bowel care
Study Procedures	
All eligible people living in the community will be invited to participate. If agreeable they will have baseline data collected and then be randomised into treatment group (transanal irrigation) or control group (standard bowel care) for six weeks. Transanal irrigation involves administration of approximately 400mL of luke-warm water via the rectum using a commercialised 'kit'. This kit includes a rectal catheter, tubing and a reservoir to hold the water. The principle is to 'flush' the lower colon clear of stool to avoid constipation and incontinence. Standard bowel care involves the use of micro enemas/suppositories, digital stimulation of the rectal sphincter, manual evacuation of stool or a combination of enemas/suppositories and digital stimulation. Outcomes will be assessed at 6 weeks post intervention by blinded assessors.

Statistical Procedures	24 participants will be required to detect a between group difference of 20 minutes on the primary outcome. This assumes

	an α level of 0.5%, a SD of 18 minutes and a correlation between pre and post values of 0.4. Regression models will be used to determine between group differences (and 95% CI). Results will be interpreted with respect to the minimally worthwhile treatment effect.
Duration of the study	The trial is expected to take approximately 2 years to complete. We anticipate the recruitment will commence in March 2021.

GLOSSARY OF ABBREVIATIONS

ABBREVIATION	TERM
ANZCTR	The Australian and New Zealand Clinical Trials Registry
CONSORT	Consolidated Standards for Reporting Trials
CRF	Case Report Forms
JWCRR	John Walsh Centre for Rehabilitation Research, University of Sydney and Northern Sydney Local Health District, Australia
NBD	Neurogenic Bowel Dysfunction
SB	Spina Bifida
SCD	Spinal Cord Disorders
SCI	Spinal Cord Injury
SBC	Standard Bowel Care
TAI	Transanal Irrigation. Introduction of water into the rectum and lower colon.

1.4 Sponsor

University of Sydney

1.5 Funding and resources

This trial is funded by a philanthropic donation and a grant from icare.

2. INTRODUCTION AND BACKGROUND

2.1 Background Information

Spinal Cord Injury (SCI) and Spina Bifida (SB) are two common causes of Spinal Cord Disorders (SCD). Both conditions can cause neurogenic bowel dysfunction (NBD) (4, 5). The severity of NBD is linked to the level of injury and 'completeness' of the lesion (6). Primary symptoms of NBD include constipation, incomplete bowel emptying and faecal incontinence (5).

A major goal of bowel care for individuals with SCD is timely and effective defaecation. This relies upon management of multiple factors. In New South Wales (NSW) and Queensland (QLD), most people with SCD are placed on a 'standard bowel care' program (7) which consists of:

- dietary management plus additional aperients to titrate stool consistency
- rectal medications (i.e. enema/suppositories) where appropriate
- digital stimulation or digital evacuation of stool
- stimulate the gastro-colonic reflex by eating breakfast before bowel care (8), and
- perform toileting at around the same time each day / second day.

Irrespective of these measures, bowel care can take a considerable amount of time and there are numerous reports in the literature to suggest that the length of time spent on bowel care can increase with time since injury (9). For example, people with NBD can spend over 90 minutes every day emptying their bowels. In addition, prolonged toileting can lead to complications such as haemorrhoids, anal fissures, dilation of the sigmoid colon, autonomic dysreflexia and pressure injuries. All can have a significant impact on physical and psychosocial wellbeing (10-14) as well as the ability to engage in vocational, recreational and social activities (15, 16). People with SCD rate bowel care as one of the most disabling aspects of SCD and of more importance to them than the inability to walk (4, 17). A particular aspect that people with SCD find most challenging is the time it takes to complete their bowel care routine (15, 18, 19) therefore it is a very disabling sequelae of SCD that requires attention.

Transanal irrigation (TAI) has been present in the Australian health care context for approximately twenty years with the biggest uptake in the paediatric and Spina Bifida population (20-22). It involves introduction of a large volume of luke - warm water (400 – 1000mL) into the rectum/lower colon via a rectal catheter which is held in place via an inflatable balloon. There are also cone shaped applicators instead of catheters. Currently, there are 3 companies that have TGA approval to provide TAI in Australia; Coloplast (Peristeen[®]), Medioplast (Navina[™]) and Sayco (Aquaflush[®]). It has only been a recent change in funding for people with chronic disability that

has made this modality of bowel management more accessible to adults with SCD and thus a feasible option for exploration as an alternative bowel care routine, particularly for those people who are experiencing complications related to bowel care or spending a prolonged time on toileting. However, there are very little accurate data upon which to guide clinical practice. In particular, there are no rigorous data to indicate whether TAI results in a clinically meaningful reduction in the time people with SCD spend on bowel care.

2.2 Research Question

Is the time to complete bowel care quicker using transanal irrigation compared to standard bowel care in adults with spinal cord disorders?

2.3 Rationale for Current Study

Bowel care is time consuming, burdensome and a negative experience for many people who have SCD. Several studies have investigated the use of TAI in populations suffering NBD in Europe and Asia however, they have mainly focussed on safety, cost-effectiveness, compliance and quality of life outcomes (23-29). In a recent Cochrane Review, Coggrave et al reported that there was evidence in favour of TAI over conservative management (standard bowel care) however, the authors concluded that it was not possible to make recommendations on best bowel care practices using any of the studies that were included in the review due to the poor methodology of the included studies (15).

their main problem. In particular, we want to attain a more precise estimate of the effect of TAI on time to complete bowel care. This will help us answer the question as to whether TAI has a clinically meaningful reduction on time spent on bowel care in individuals presenting with this problem.

3 STUDY OBJECTIVES

3.1 Primary Objective

The primary aim of this study is to determine if TAI reduces time spent on toileting (as determined by blinded assessors) in adults with chronic SCD living in NSW/QLD.

3.2 Secondary Objectives

The secondary objectives are to determine if TAI in adults with chronic SCD living in NSW/QLD:

- reduces time spent on toileting (as determined by participants with the use of diaries)
- reduces constipation
- reduces faecal incontinence
- improves quality of life
- improves perceptions of effectiveness of bowel care routines
- reduces the burden of bowel care

4. STUDY DESIGN

4.1 Type of Study

A pragmatic, prospective, community based, single blinded randomised controlled trial.

4.2 Study Design

The trial will be a community based, randomised controlled trial. All eligible participants will be invited to participate. Participants will be randomised to either transanal irrigation (TAI) (intervention) or standard care (control).

Participants allocated into the intervention group will commence transanal irrigation including training and support from a Registered Nurse with experience in the procedure. All aspects of transanal irrigation will be individualised to the participant as is current practice when establishing a routine with TAI. Participants allocated into the control group will continue with their current bowel care routines.

The primary outcome will be time to complete routine bowel care at six weeks.

Participants will not be blinded to their group allocation because of the nature of the system and the need for participant / carer training, however, the assessor will be blinded to group allocation.

All participants will continue to receive all non-rectal interventions that constitute 'usual or standard care'. This includes the use of oral aperients, adequate fluid intake, and appropriate dietary intake, timing of bowel care and pr checks and digital stimulation as required (31).

All design features important for minimising bias will be adhered to and the trial will be registered with The Australian and New Zealand Clinical Trials Registry (ANZCTR). The minimally worthwhile treatment effect and statistical analyses will be set prior to the commencement of the trial in accordance with best practice. All relevant details enabling the compilation of a CONSORT flow diagram will be recorded and reported.

4.2 Number of Participants

Twenty four.

4.3 Study sites

The study is community based; therefore, participants will be recruited from either the spinal outpatient departments of Royal North Shore Hospital and Prince of Wales Hospital or via the community.

All study nurses will receive education and training on the set up and use of the 3 main transanal irrigation systems and this will be supported with a procedural document to ensure consistency.

It is anticipated that 12 participants will be recruited from New South Wales and 12 participants from Queensland.

4.4 Expected Duration of Study

The trial is expected to commence on 1st March 2021, with recruitment expect to take up to 24 months. Assuming recruitment continues until 1st March 2023, the final data collection will occur mid April 2023.

4.5 Primary and Secondary Outcome Measures

One primary and 6 secondary outcomes will be used. Most outcomes will be collected on two occasions at baseline and at six weeks post randomisation. The exceptions are two outcomes which will be collected on two occasions but at six weeks only: The *Global impression of change and Burden of treatment*. The other exception is the *time to complete bowel care (participant determined)*. This outcome will be collected using diaries over the week preceding the baseline and six week assessments.

Primary outcome:

1. *Time to complete bowel care (assessor determined)*: The time from commencement of the enema/irrigation administration procedure to completion of faecal elimination as defined by an empty rectum on per rectum (pr) check. This will be assessed 4 times: on two occasions (2 separate days) at baseline (after randomisation) and on two occasions at week 6 (upon completion of the trial). The two measurements taken at each time point will be averaged to attain one score for each time point.

Secondary outcomes:

1. *Time to complete bowel care (participant determined)*: The time from commencement of the enema/irrigation administration procedure to completion of faecal elimination as defined by an empty rectum on per rectum (pr) check. The participants will be required to use a stopwatch /timer to time bowel care on two occasions (2 separate days) at baseline (after randomisation)

and on two occasions (2 separate days) at week 6 (upon completion of the trial). These occasions will be on days that blinded assessment will NOT occur. Participants will be required to enter the bowel care times into a diary. The two measurements taken at each time point will be averaged to attain one score for each time point.

2. *Severity of constipation*: This outcome captures the severity of constipation. It will be measured using the Cleveland Clinic Constipation Scoring System (CCCS) (32). This is an 8-item self-report questionnaire. Participants are required to respond to questions such as *“completeness: Feeling incomplete evacuation: on a Likert scale (0-4) anchored with the following words “never”, rarely”, “sometimes”, “usually”, “always”*. Total scores range from 0-30 (30 being the most severe symptoms of constipation). This will be assessed 4 times: twice prior to commencing the trial (baseline) and twice in week 6 (upon completion of the trial). Measurements will be averaged to attain one score for each endpoint.

3. *Frequency of unplanned bowel evacuations*: This outcome captures faecal incontinence outside of regular bowel care. It will be measured using the Vaizey (St Mark’s) Faecal Incontinence Scale (33). This is a 7-item self-report questionnaire with an overall score ranging from 0-24 (0 = perfect continence, 24 being totally incontinent). Participants will be required to respond to questions such as *“in the past 4 weeks I had incontinence of solid stool”* on a Likert scale (0-4) anchored with the following words *“never”, “rarely”, “sometimes”, “weekly”, “daily”*. This will be assessed 4 times: twice prior to commencing the trial (baseline) and twice in week 6 (upon completion of the trial). Measurements will be averaged to attain one score for each endpoint.

4. *Spinal Cord Injury Quality of Life (SCI QoL) – Bowel Management Difficulties*: (34) This outcome captures quality of life due to bowel management difficulties. It will be measured using the SCI QoL. This is a 9-item self-report questionnaire with an overall raw score ranging from 9 to 45. Participants are required to respond to statements such as *“I was frustrated by repeated bowel accidents”* on a Likert Scale (1-5) anchored with the following words: *“not at all”, “a little bit”, “somewhat”, quite a bit” and “very much”*. This will be assessed 4 times: twice prior to commencing the trial (baseline) and twice in week 6 (upon completion of the trial). The total raw score will be converted into a T score (see, Table 9 (34)) where a higher score is indicative of a worse outcome. Measurements will be averaged to attain one score for each endpoint.

5. *Global impression of change in bowel function (Participant reported)* (35): This outcome captures participants’ perception of how much their bowel function has changed over the last six weeks. It will be measured using a 15-point Scale. Scores will be anchored at each end from -7 *“very much worse”* 0 *“no change”* to 7 *“very much better”*. Participants will be asked:

Do you think there has been a change for better or worse in any aspects of your bowel function or bowel routine over the past 6 weeks? Please rate from -7 to 7 where -7 indicates “very much worse” 0 indicates “no change” and 7 indicates “very much better”.

This will be assessed twice in week 6 (upon completion of the trial). Measurements will be averaged to attain one score for this endpoint.

6. *Burden of treatment questionnaire*. This outcome is designed to measure the level of burden participants feel around the treatment for their neurogenic bowel dysfunction over the past 6

weeks. It will be measured using an 11-point Likert Scale (0-10) anchored at each end from “not at all bothersome” to “extremely bothersome”. Participants will be asked:

How bothersome have you found managing your bowel routine over the last 6 weeks? Please rate on the below scale from 0 to 10 where 0 indicates “not at all bothersome: and 10 indicates “extremely bothersome”.

This will be assessed on two occasions at week 6 (upon completion of the trial). Measurements will be averaged to attain one score for each endpoint.

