6.4 Enrolment and Randomisation Procedures

Participants will be enrolled into the study after the informed consent process has been completed. Because half of the participants will be randomised into the control group, procurement and training of the preferred TAI system will occur *prior* to randomisation for each participant so that the control arm will be able to commence TAI as soon as they complete the study if they wish to. The investigator responsible for collecting the baseline data will check that each participant meets the inclusion criteria. They will collect and confirm all demographic information including date of birth, sex, details about the injury/condition, including date of injury as well as a SCI bowel function data set. Baseline data on the primary and 4 of the 6 secondary outcome measures will be also be collected prior to randomisation.

A secure random-allocation schedule will be computer-generated prior to commencement of the trial by an independent person and kept at a central off-site location. The randomisation schedule will be blocked (1:1) to ensure equal numbers of participants are randomised to the treatment and control arms. A participant will be entered into the trial when baseline details are logged, and the allocation is provided. At this point, the participant will receive a study number, and this will be documented on all study documents.

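### Burden of treatment is a level score that could be asked at baseline but is collected at week 6 only, which gives up precision and any check on chance imbalance for this secondary outcome

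*Protocol*

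**What the plan says.** Section 4.5 of the protocol collects most outcomes at baseline and at six weeks, and then makes an exception for the Global Impression of Change and Burden of treatment: "The exceptions are two outcomes which will be collected on two occasions but at six weeks only". The definition of Burden, secondary outcome 6 in the same section, repeats that it is rated twice at week 6 and averaged. Section 6.4 agrees: "Baseline data on the primary and 4 of the 6 secondary outcome measures" are to be taken before randomisation, which leaves out these same two.

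The Burden item reads "How bothersome have you found managing your bowel routine over the last 6 weeks". On the scale, the protocol says "It will be measured using an 11-point Likert Scale (0-10) anchored at each end". The objective it serves, in section 3.2, is that TAI "reduces the burden of bowel care". The synopsis plans 24 participants, 12 per arm. Section 6.4 describes 1:1 blocking and mentions no stratification. The visit schedule in section 7 has no row for Burden at any visit.

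**The concern.** The exception in section 4.5 covers two different kinds of item. The Global Impression of Change asks how bowel function has changed over six weeks, so it has no meaning at entry. Burden asks for a level. Its wording mentions neither TAI nor the trial, and it fits any six-week period. Every participant arrives with an established routine: section 6.2.1 requires more than 30 minutes on toileting plus a further problem, and section 4.2 has controls carry on as they are. The question can therefore be answered in full at baseline. The protocol gives no reason for omitting it.

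With 12 per arm, bother at entry can differ noticeably between arms by chance. Without a baseline rating, nobody can see that difference on this scale or adjust for it, and a possible gain in precision is given up. No later analysis plan can recover a baseline that was never taken.

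**Working it through.** **Inputs.** From the protocol: 12 per arm (synopsis); regression models with 95% CIs (section 11.3). Assumed: r, the correlation between the averaged baseline and averaged week-6 Burden scores, which is not in the protocol; equal SDs at both times; approximate normality; complete data. Results are in units of the Burden SD.

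**The plan's own figure.** N = 24 is derived for the primary outcome. With a difference of 20 minutes, SD 18, r = 0.4 (synopsis), two-sided alpha 0.05 and 80% power:
- adjusted SD = 18 × √(1 − 0.4²) = 16.5
- n per arm = 2 × (1.960 + 0.842)² × 16.5² / 20² = 10.7, so 11 per arm and 22 in total
- with 5% dropout, 22 / 0.95 = 23.2, so 24.

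This reproduces. With r = 0.04, as section 11.1 states, the same steps give 13 per arm and 28 in total, which does not. That discrepancy is a separate matter. Here it shows that the planned N fits a calculation that uses baseline adjustment for the primary outcome, and that 0.4 is not a firm value even there.

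**Chance imbalance at baseline.** The SE of the difference in baseline means is √(2/12) = 0.408 SD. So P(|imbalance| > 0.5 SD) = 2 × [1 − Φ(0.5/0.408)] = 0.22.

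**How much reaches week 6.** The expected shift in the week-6 difference is r × imbalance.

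**Precision.** The 95% CI half-width without a baseline is t(0.975; 22 df) × 0.408 = 0.847 SD. With baseline as covariate it is t(0.975; 21 df) × √(1 − r²) × 0.408 × √(1 + 1/20). The last factor is the average cost of estimating the slope. The difference detectable with 80% power without a baseline is 1.20 SD.

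| Assumed r | Shift from a 0.5 SD imbalance | Adjusted half-width | Ratio to 0.847 | Detectable difference, adjusted |
|---|---|---|---|---|
| 0.04 | 0.02 SD | 0.869 SD | 1.027 | 1.23 SD |
| 0.2 | 0.10 SD | 0.852 SD | 1.007 | 1.20 SD |
| 0.4 | 0.20 SD | 0.797 SD | 0.942 | 1.13 SD |
| 0.6 | 0.30 SD | 0.696 SD | 0.822 | 0.98 SD |
| 0.8 | 0.40 SD | 0.522 SD | 0.617 | 0.74 SD |

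**Validity.** In 100,000 simulated trials per value of r with no true effect, the unadjusted week-6 comparison rejected in 4.9% (r = 0.4) and 5.0% (r = 0.6), and the mean estimate was zero to within 0.001 SD. Among the roughly 22% of trials with an imbalance above 0.5 SD, it rejected in 8% (r = 0.4) and 13% (r = 0.6). With adjustment, rejection in those trials was about 5%.

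**The case against.** A reader might infer that the Burden comparison is biased, or that a chance imbalance is confounded with the treatment effect so that the result cannot be interpreted. The protocol does not support that. Allocation is randomised 1:1, so the week-6 difference is unbiased without a baseline. Its CI already allows for chance imbalance, and the overall false-positive rate stays at 5%. The higher rates above apply only to the subset of trials with a large imbalance. Nor does an imbalance pass through whole: at r = 0.4, a 0.5 SD imbalance moves the result by 0.20 SD, against a half-width of 0.85 SD.

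The gain may also be nil. One arm changes its rectal treatment between the two ratings, so a low r is plausible. The 0.4 in the synopsis belongs to a different outcome and is contradicted by section 11.1. Quoting only √(1 − r²) would give narrowing of 8% at r = 0.4 and 20% at r = 0.6. Allowing for the lost degree of freedom and the slope estimate reduces these to 6% and 18%.

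Related measures are taken at baseline: SCI-QoL Bowel Management Difficulties and the Neurogenic Bowel Dysfunction Score. They could show part of an imbalance and could serve as covariates, but they ask different questions and are only partial proxies.

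The protocol is consistent on timing, and the objective of reducing burden can be met by a between-group comparison without within-person change. Both points stand, so this is an avoidable loss and not a contradiction. A six-week recall at baseline would overlap the TAI training given before randomisation and might be coloured by it. That applies to both arms alike and does not prevent the score from serving as a covariate.

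**Conclusion.** The point holds as a cheap improvement to one secondary outcome. Burden could be measured at baseline, and the protocol gives no reason for not doing so. The cost of the omission is lost precision and no direct view of imbalance at entry; validity is not at stake. Its size rests on an assumed r: about no gain in CI width at r = 0.2, 6% at r = 0.4, 18% at r = 0.6, and a slight loss if r is near zero. The 22% chance of an imbalance above 0.5 SD follows from 12 per arm alone and is not itself a measure of harm. The criticism does not extend to the Global Impression of Change, for which a six-week-only rating is right, or to the primary outcome.

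**What to change.** - Section 4.5: limit the six-week-only exception to the Global Impression of Change. Ask the same 0-10 Burden question at both baseline visits, average the two ratings, and use the average as a covariate in the week-6 regression.
- Timing: take both ratings before randomisation, in line with section 6.4. The section 7 schedule places randomisation at the second baseline visit, so at that visit the question must come before the allocation is disclosed. Section 4.5 describes the baseline timings of bowel care as taken after randomisation; the Burden text should not copy that.
- Section 6.4: change the count of secondary outcomes with a baseline from 4 to 5 of the 6.
- Section 7: add a Burden row, now absent, at the two baseline and two six-week visits.

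The cost is one extra question at two visits that already take place, a small edit to the protocol and case report form, and one degree of freedom in the analysis. If r proves low, there will be little or no gain in precision, but imbalance at entry can still be described.

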6.5 Blinding Arrangements

It is not possible to blind the participants, study nurses or carers to allocation. However, all assessors will be blinded. Additionally, all Associate Investigators will remain blinded. To ensure this, the study nurses, participant and / or carers delivering the bowel care will be asked not to discuss any aspects of their bowel care with the associate investigator(s). The success of blinding for the assessor/s will be checked following the 6-week assessment.

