7 STUDY VISITS AND PROCEDURES SCHEDULE

Procedure Schedule	Screening and recruitment	Assessment at baseline		Intervention	Assessment at 6- weeks post randomisation	
	-6 to -1 week	-7 to 0 days		Week 1 - 6	Week 7	
Protocol Activity:		1st visit	2nd visit		1st visit	2nd visit
Informed Consent	✓					
Eligibility Checklist	✓					
Demographic details	✓					
Procure TAI Device	✓					
Training on how to use TAI	✓					
Randomisation			✓			
Adverse Events Check		✓	✓	✓✓✓✓✓✓	✓	✓
Outcome measures:						
Neurogenic Bowel Dysfunction Score		✓	✓		✓	✓
Time to complete bowel care (assessor)		✓	✓		✓	✓
Time to complete bowel care (participant)		✓	✓	✓✓		
CCCSS		✓	✓		✓	✓
St Mark's Scale		✓	✓		✓	✓
SCI-QOL, BMD		✓	✓		✓	✓
Global Impression of Change					✓	✓
Blinding question Assessor		✓	✓		✓	✓
End of Study checklist						✓

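### Section 4.5 places the baseline timing of the primary outcome after randomisation, contradicting Section 6.4 and the synopsis, which place it before

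*Protocol*

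**What the plan says.** Protocol Section 4.5 defines the primary outcome as the assessor-timed duration of bowel care and fixes its measurement: "This will be assessed 4 times: on two occasions (2 separate days) at baseline (after randomisation". The two baseline values are averaged. The entry for the participant-timed secondary outcome carries the same bracketed timing. The questionnaire outcomes in Section 4.5 are worded differently: "twice prior to commencing the trial (baseline) and twice in week 6 (upon completion of the trial".

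Section 6.4 gives the opposite order: "Baseline data on the primary and 4 of the 6 secondary outcome measures will be also be collected prior to randomisation". It then says: "A participant will be entered into the trial when baseline details are logged, and the allocation is provided". The synopsis agrees with Section 6.4: "If agreeable they will have baseline data collected and then be randomised into treatment group (transanal irrigation) or control group".

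The schedule in Section 7 puts the two baseline visits in a window of days -7 to 0, ahead of a separate column for the intervention in weeks 1 to 6. Randomisation is ticked at the second baseline visit, with no order given against the timing done at that visit.

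Two other statements bear on the point. On preparation for TAI, Section 6.4 says "procurement and training of the preferred TAI system will occur" before randomisation. Section 6.5 says "It is not possible to blind the participants, study nurses or carers to allocation".

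**The concern.** The two orders cannot both be followed, and the conflict sits in the definition of the primary outcome. Because the questionnaires are described differently, a site could reasonably take the bracketed timing for the two timed outcomes as deliberate.

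A baseline taken after allocation is no longer protected by randomisation. Participants and carers would know the arm. They would already have the device and the training, so TAI might have begun. Even without that, knowing the arm could alter behaviour, or the participant's own stopwatch timing. If the week-6 result is then adjusted for this baseline, part of the treatment effect, or of a reaction to allocation, is adjusted away or added. With 24 participants and a single baseline period, a contaminated baseline cannot be recovered later.

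**Working it through.** **The texts side by side**

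| Place | Order given |
|---|---|
| Section 4.5, primary outcome | baseline after randomisation |
| Section 4.5, participant-timed outcome | baseline after randomisation |
| Section 4.5, questionnaires | baseline before the trial starts |
| Section 6.4 | baseline before randomisation; allocation given when baseline is logged |
| Synopsis | baseline, then randomisation |
| Section 7 | randomisation ticked at second baseline visit; order within the visit not stated |

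The count in Section 6.4, four of six secondary outcomes, includes the participant-timed one: the two left out are the global impression of change and the burden question, which Section 4.5 collects at week 6 only. So Section 6.4 contradicts both entries in Section 4.5.

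**Does the design rely on baseline?** Section 11.3 says only that regression models will be used. The sample size is more informative.

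Inputs: difference 20 minutes, SD 18 minutes, power 80%, alpha 0.05 (taken as two-sided), dropout 5% (Section 11.1); 1:1 allocation (Section 6.4); correlation 0.4 (synopsis) or 0.04 (Section 11.1). The synopsis also prints a different alpha; the value in Section 11.1 is used here.

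Formula, normal approximation: n per arm = 2 × (1.960 + 0.842)² × V / 20², where V = 18² × (1 − r²) for a baseline-adjusted comparison.

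- r = 0.4: V = 324 × 0.84 = 272.2; n = 10.7, so 11 per arm and 22 in total; 22 / 0.95 = 23.2, so **24**. This matches the plan.
- r = 0.04: V = 324 × 0.9984 = 323.5; n = 12.7, so 13 per arm and 26 in total; 26 / 0.95 = 27.4, so 28. No match.
- Change score at r = 0.4: V = 2 × 324 × 0.6 = 388.8; n = 15.3, so 16 per arm and 32 in total; 34 after dropout. No match.

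The planned 24 therefore reproduces as a baseline-adjusted comparison with r = 0.4. That supports, but does not prove, that baseline is meant to be a covariate.

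**What a contaminated baseline would do.** Suppose the TAI arm's baseline is already shorter by s minutes. With equal SDs before and after, the within-arm slope equals r, so:

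adjusted difference = 20 − r × s

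The documents give no value for s. The range below, 5 to 20 minutes, is an assumption (a quarter, a half and all of the planned effect).

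| s (minutes) | r = 0.4: loss, adjusted effect | r = 0.04: loss, adjusted effect |
|---|---|---|
| 5 | 2, 18 | 0.2, 19.8 |
| 10 | 4, 16 | 0.4, 19.6 |
| 20 | 8, 12 | 0.8, 19.2 |

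At 12 per arm and r = 0.4, normal-approximation power is 84% with no shift, and 76%, 66% and 43% for the three rows. At r = 0.04 it is 78% with no shift and 74% in the last row. These figures leave out the extra variance that a baseline imbalance between arms brings. A shift in the other direction would enlarge the estimate by the same arithmetic.

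An unadjusted comparison at week 6 does not use the baseline and would not be biased in this way.

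**The case against.** The strongest reply is that the protocol shows its intention elsewhere. Section 6.4, the synopsis and the day -7 to 0 window all point to a baseline before randomisation, and Section 4.5 itself has the participants' diary kept in the week before the baseline assessment. The bracketed words look like a drafting slip. That is probably right, and it shows which text to correct. It does not make the correction optional, because the slip appears twice, one of them in the primary outcome definition, and the schedule leaves the order within the second visit open.

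Some stronger readings do not stand:

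- A reader might infer that the trial will lose 8 minutes of effect. No text says irrigation starts before the baseline timings, and the separate intervention column in Section 7 argues against it. The 20-minute shift is an assumed upper bound.
- A reader might infer that a change-score analysis would show no effect. The protocol does not plan one.
- A reader might see "Training on how to use TAI" ticked in the screening column and conclude that even a pre-randomisation baseline is spoiled. Training precedes allocation and applies to both arms, so it cannot cause a difference between arms at baseline, and nothing says it replaces usual care. Section 6.4 also gives a reason for it: controls can start TAI once they finish.
- A reader might say that the error unblinds the assessor. The same question arises at week 6, when TAI is in use, so it is not specific to the baseline wording.

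**Conclusion.** Wrong as written. Section 4.5 contradicts Section 6.4 and the synopsis on when baseline is timed, for the primary outcome and for the participant-timed secondary outcome, and Section 7 does not settle the order within the second visit. This conclusion needs no figure.

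The possible bias is conditional. It requires that Section 4.5 is followed, that TAI or knowledge of allocation shifts the baseline in one arm, and that the analysis adjusts for baseline, which is inferred from the sample size. On those assumptions the loss from a 20-minute effect is 2 to 8 minutes at a correlation of 0.4 and under 1 minute at 0.04. The documents do not support a claim that such a shift will occur.

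**What to change.** In Section 4.5, replace *after randomisation* with *before randomisation* in the entries for the primary outcome and the participant-timed secondary outcome. In Sections 6.4 and 7, state that allocation is released only after the second baseline timing has been logged.

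The cost is a protocol amendment to wording. It adds no visits, staff or participants, and the sample size stays at 24. Nothing here calls for moving the baseline visits ahead of TAI training. That would change the schedule, could put baseline up to six weeks before randomisation, and might weaken the pre-post correlation the sample size relies on.
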